4 STUDY DESIGN

Description: This observational study will assess the feasibility of implementing COVID-related testing and triage procedures in the dental setting to ensure the safety of DHCWs and patients. Results from this study may provide preliminary data to inform a larger network-wide study grant application.

This study will be conducted in four (4) private practice dental offices, each of which with at least one National Dental Practice Based Research Network (PBRN) member dentist. Based upon preference of the Practice Based Research Network dentist, offices will participate as either a Point of Care (POC) Office (2 offices) or a LAB office (2 offices). In the POC offices, we will test procedures for POC/SARS-CoV-2 antigen testing in DHCWs and patients of the practice along with enhanced triage using pulse oximeters. In the LAB offices, DHCWs and patients will test procedures for a saliva-based laboratory SARS-CoV-2 viral test (LAB) along with enhanced triage methods. The National Dental PBRN dentist and office will choose to participate in either the POC or LAB group; offices will not be assigned to study groups.

Study Population: The study population for this study will be all dentists, hygienists, dental assistants and dental office personnel (e.g., dentists, hygienists, dental assistants, front office staff) working in a participating dental office, as well as patients being treated in the participating dental office.

Important Outcomes: For this study, important outcomes include percent of both DHCW and patients willing to participate percent completing the protocol. See Section 3 for more detail.

Number of Study Groups: Four (4)

1. DHCW in POC Offices
2. Patients in POC Offices
3. DHCW in Lab Offices
4. Patients in Lab Offices

Expected Duration of Subject Participation:

DHCWs (in POC or LAB Offices) - 1 month
Patients (in POC or LAB Offices) - 2 weeks

Sequence of Procedures and Duration of Study Period: See Section 7.

5 STUDY POPULATION

5.1 Participant Inclusion Criteria

A **Dental Health Care Worker** must meet all of the following criteria to be eligible to participate in the study:

- Be 18 years or older
- Be a National Dental PBRN member dentist or work in a dental office with a National Dental PBRN member dentist who consents to study participation
- Be able to understand the informed consent.
- Provide signed and dated informed consent form
- Be able to understand all instructions for data collection instruments
- Be willing and able to comply with all study procedures, including COVID-19 testing, and be available for the duration of the study

A **Patient** must meet all of the following criteria to be eligible to participate in the study:

- Be 18 years or older
- Be able to understand the informed consent.
- Have a computer or electronic tablet with internet access
- Able to complete consent and questionnaire on a computer or electronic tablet
- Provide signed and dated informed consent form
- Be able to understand all instructions for data collection instruments
- Be willing and able to comply with all study procedures, including having a COVID-19 test performed

5.2 Participant Exclusion Criteria

Participants would be excluded if they participated in the feasibility study previously conducted at Rutgers University.

5.3 Strategies for Recruitment and Retention

Target Sample Size: 40 dental care health workers and 80 patients.

Target Sample Size by Gender, Race, Ethnicity, and Age: Study population will be drawn from National Dental PBRN dentist members, their co-workers and patients seen in their office. Any adult 18 years and older meeting the inclusion criteria and not meeting any exclusion criteria will be eligible to participate. It is expected that the mix of gender, race and ethnicity will reflect the patient mix of the participating dental offices.

Study Population: The DHCW study population will be dentists, hygienists, assistants and office staff who work in an office with a National Dental PBRN member dentist. The patient study population will be drawn from the dental practice with the National Dental PBRN member dentist.

Inclusion of Women and Minorities and Individuals of All Ages:

Women: Women will be included in this study.

Minorities: Minorities will be included in this study.

Recruitment Strategies: Four (4) National Dental PBRN practitioners who have 4 or more DHCW in their office will be recruited to participate by the National Dental PBRN Node Coordinator. The Node Coordinator will then recruit DHCWs within the practice to participate. If a practice is unable to consent at least 5 DHCWs, the practice will not participate in the study. Another National Dental PBRN practice will be recruited to participate.

Patients will be sent a letter about 4 weeks prior introducing the study by the PBRN practitioner. The PBRN practitioner or PBRN investigators in the office will reach out to patients by phone about 2 weeks prior to the dental visit. The study will be explained and if the patient is interested, an e-mail link will be sent which will allow the patient to review the informed consent. A phone number will be provided to answer questions.

Recruitment Protocol (All Study Groups):

The PRBN Node Research Coordinator will recruit PBRN dentist members to participate in the protocol. The PBRN Node Research Coordinator will contact PBRN dentist members to introduce the study and gauge initial interest. The dental office will be enlisted if the PBRN dentist member and 4-9 additional office DHCWs of the practice are willing to participate and the PBRN member is willing to perform the responsibilities of the protocol including enrolling and completing 10 patients. The PBRN practitioner's preference will determine which protocol (POC or LAB) will be followed in the office. In total, two POC offices will participate, and two LAB offices will participate.

Office	Study Group	Protocol	COVID-19 Related Tests (Method)
POC	1- DHCW in POC Offices	POC DHCW Protocol	
• Antigen (nasal swab)• Antibody (capillary blood)
	2- Patients in POC Offices	POC Patient Protocol	
• Antigen (nasal swab)
LAB	3- DHCW in Lab Offices	LAB DHCW Protocol	
• Virus (saliva and/or tongue)• Antibody (capillary blood)
	4- Patients in LAB Offices	LAB Patient Protocol	
• Virus (saliva)

Retention: In order to minimize loss of study participants and/or incomplete data collection, the following activities will take place:

- Node Coordinators will work with National Dental PBRN study participants responsible for recruiting subjects and completing surveys to encourage patient enrollment and study completion.
- Participants will receive compensation.

Compensation and Scheduled Payments: DHCWs who complete the study procedures including the end-of-study survey will receive \$125 each. Patients who complete the LAB study procedures including the post-visit survey will be provided \$100 and patients who complete the POC study procedures including the post-visit survey will be provided \$50.

Additional Plans to Minimize Missing or Incomplete Data: The following will minimize missing or incomplete data:

- When appropriate, REDCap survey data fields are set to "required".
- REDCap validation rules on data fields to limit responses to those which are valid

5.4 Participant Withdrawal or Discontinuation from Study Procedures/ Intervention

5.4.1 Reasons for Participant Withdrawal or Discontinuation from Study Procedures/ Intervention

Participants are free to withdraw from participation in the study at any time upon request.

An investigator may discontinue an individual's participation in an intervention or withdraw an individual from the study if:

- The participant has a serious adverse event requiring hospitalization.

- Any clinical adverse event (AE), laboratory abnormality, or other medical condition or situation occurs such that continued participation in the study would not be in the best interest of the participant.
- The participant meets an exclusion criterion (either newly developed or not previously recognized) that precludes further study participation.

5.4.2 *Handling of Participant Withdrawals from Study*

Participants may withdraw participation consent at any time, either verbally or in writing. Participants who further withdraw their consent for the use of data already collected must do so in writing. The Node Coordinator will interview the participant and document the withdrawal of consent using the Consent Withdrawn Received Form in the REDCap system. Documentation includes the date, the reason for participant withdrawal, as well as the upload of any written withdrawal request. Upon withdrawal, all study procedures would cease, however, the participant would be offered continued care as part of the normal standard of care.

Participants who withdraw will not be replaced.

5.5 Premature Termination or Suspension of Study

This study may be suspended or prematurely terminated if there is sufficient reasonable cause. Written notification, documenting the reason for study suspension or termination, will be provided by the suspending or terminating party to [name] and the funding agency (NIDCR). The principal investigator will also promptly inform the sIRB and NIDCR and will provide the reason(s) for the termination or suspension.

Circumstances that may warrant termination include, but are not limited to:

- Determination of unexpected, significant, or unacceptable risk to participants.
- Insufficient adherence to protocol requirements.
- Data that are not sufficiently complete and/or evaluable.
- Determination of futility.

6 STUDY SCHEDULE

6.1 Dental Health Care Worker Subjects

The following is the schedule of events for Dental Health Care Worker Subjects in the POC Offices.

Visit	Day	Dental Health Care Worker Subjects Activities Performed
Enrollment (15 minutes)	Day -28 (+/- 29 days)	
 • Obtain written Informed Consent
Start-of-Study (35 minutes)	Day 0	
 • Complete Start-of-Study Survey • Complete Start-of-Study Triage Case Report • Undergo POC (antigen) COVID-19 test • Provide specimen for ELISA (antibody) test
Mid-Study (20 minutes)	Day 14 (+/- 7 days)	
 • Complete Mid-Study Triage Case Report • Undergo POC Covid-19 Test
End-of-Study (40 minutes)	Day 28 (+/- 14 days)	
 • Complete End-of-Study Triage Case Report • Undergo POC COVID-19 Test • Provide specimen for ELISA (antibody) test • Complete End-of-Study Survey • Complete DHCW Participation Questionnaire

The following is the schedule of events for Dental Health Care Worker Subjects in the LAB Offices.

Visit	Day	Dental Health Care Worker Subjects Activities Performed
Enrollment (15 minutes)	Day -28 (+/- 29 days)	
 • Obtain written Informed Consent
Start-of-Study (35 minutes)	Day 0	
 • Complete Start-of-Study Survey • Complete Start-of-Study Triage Case Report • Provide specimen(s) for PCR (viral) test • Provide specimen for ELISA (antibody) test
Mid-Study (20 minutes)	Day 14 (+/- 7 days)	
 • Complete Mid-Study Triage Case Report • Undergo POC Covid-19 Test
End-of-Study (40 minutes)	Day 28 (+/- 14 days)	
 • Complete End-of-Study Triage Case Report • Provide specimen(s) for PCR (viral) test • Provide specimen for ELISA (antibody) test • Complete End-of-Study Survey • Complete DHCW Participation Questionnaire

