 - Questions include demographics, PPE used in the office, work practice controls used in the office, importance of triage and testing, importance of PPE measures, perceptions of safety and comfort in the workplace, safety culture in the office, SARS-CoV-2 testing preferences, dentists' role in SARS-CoV-2 testing, and willingness to test in the office
- Undergo a three-part COVID-19 triage screening*
 - Symptom questions
 - Presence or absence of:
 - fever or chills
 - cough
 - shortness of breath or difficulty breathing
 - fatigue
 - muscle and body aches
 - headache
 - loss of taste

- loss of smell
- sore throat
- congestion or runny nose
- nausea or vomiting
- diarrhea
- Temperature check
- Pulse oximeter reading
- Complete two COVID-19 related tests**
 - SARS-CoV-2 PCR viral test
 - Saliva (self-collected) and tongue specimens (collected by PBRN practitioner, designated investigator or self)
 - ELISA Antibody test (specimen collected by PBRN practitioner, designated investigator or self)
 - A small lancet will create a finger prick to collect a small blood sample for collection using a Mitra cartridge (blood specimen collection device)
 - The Mitra cartridge will be packaged by the DHCW and placed in the practice collection box to await shipment to Rutgers
 - The sample will be processed by the Public Health Research Institute (PHRI) Lab at Rutgers

Mid-Study- Day 14 (+/- 7 days)

- Undergo a COVID-19 triage screening in the office*
- Complete a SARS-CoV-2 PCR Viral test**
 - Saliva (self-collected)

[figure not shown]
End of Study- Day 28 (+/- 7 days)

- Undergo a three-part COVID-19 triage screening*
 - Symptom questions
 - Temperature check
 - Pulse oximeter reading
- Complete two SARS-CoV-2 tests**
 - SARS-CoV-2 PCR viral test
 - Saliva (self-collected) and tongue specimens (collected by PBRN practitioner, designated investigator or self)
 - ELISA Antibody test (specimen collected by PBRN practitioner, designated investigator or self)
 - A small lancet will create a finger prick to collect a small blood sample for collection using a Mitra cartridge (blood specimen collection device)
 - The Mitra cartridge will be packaged by the DHCW and placed in the practice collection box to await shipment to Rutgers
 - The sample will be processed by the Public Health Research Institute (PHRI) Lab at Rutgers
- Complete two electronic surveys:

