 - *DHCW End of Study Survey*- Questions include importance of triage and testing, importance of PPE measures, perceptions of safety and comfort in the workplace, safety culture in the office, SARS-CoV-2 testing preferences, dentists' role in SARS-CoV-2 testing, willingness to test in the office, and vaccinations
 - *DHCW Participation Survey*- Questions explore perceptions related to study participation including survey and testing logistics

*If any aspect of the COVID-19 triage screening is positive without any preexisting condition which could explain the positive screening (i.e., a history of hay-fever which likely explains sneezing or a report of physical activity which likely explains muscle soreness), the DHCW will be referred to their primary care physician for further testing.

- Positive screening includes having one or more symptoms of unknown origin
- A positive temperature is considered greater than 100.4 degrees F
- A positive pulse oximeter is considered when the blood oxygen saturation level is below 95%

**If the lab processed SARS-CoV-2 test is positive, the DHCW may be dismissed from duties and instructed to consult with their primary care provider for further testing.

Group 4- Patients in LAB Offices

Consent Process for Group 4 - Patients in LAB Offices

Three weeks (+/- 14 days) prior to a scheduled dental visit, patients will get an introductory/interest letter, informing patients about the study and that they may be receiving a phone call to determine their interest. About two weeks prior to their scheduled dental visit, patients will be contacted by the dental office to determine their willingness to participate in the study. Patients who indicate interest will be sent an email link, which opens the consent. Patients will be able to speak to the PBRN practitioner or approved staff member with any questions or seek clarifications. The consent will clearly outline participant expectations and offer the opportunity for potential participants to contact the office for more information as needed. Participants who elect to participate will affirm their willingness to participate by clicking the “*I agree to take part in this study*” button at the end of the consent form.

Study Procedures for Group 4 - Patients in LAB Offices

Study participants will be asked to do the following:

[figure not shown]
- Two weeks before the dental visit
 - Complete and sign electronic consent
 - Complete an electronic survey: *Patient Pre-Visit Survey*

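### Section 6.1 schedules a point-of-care test for LAB-office workers at Day 14, where Section 7 requires a self-collected saliva PCR

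*Combined protocol and SAP*

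**What the plan says.** Section 6.1 has two DHCW schedules, one for each office type. The second is introduced by "The following is the schedule of events for Dental Health Care Worker Subjects in the LAB Offices". It places PCR and ELISA specimens at Day 0 and Day 28. At Day 14 (+/- 7 days) it lists a triage report and "Undergo POC Covid-19 Test". The Mid-Study row of the POC-office table above it is worded identically.

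Section 7, Group 3 (DHCWs in LAB offices), has the same visit and the same window. There the instruction is "Complete a SARS-CoV-2 PCR Viral test", and the only specimen named is "Saliva (self-collected", with no tongue specimen. Days 0 and 28 call for saliva and tongue specimens together.

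Other places bear on which test is intended:

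- Section 4: "In the LAB offices, DHCWs and patients will test procedures for a saliva-based laboratory SARS-CoV-2 viral test (LAB". The same section directs the reader onward: "Sequence of Procedures and Duration of Study Period: See Section 7".
- Section 5.3, test table, LAB DHCW row: "Virus (saliva and/or tongue", plus antibody. Antigen is listed only for the two POC groups.
- Section 7, Group 3 footnote: "If the lab processed SARS-CoV-2 test is positive, the DHCW may be dismissed from duties".
- Section 7.1, Group 3, Testing Case Reports: Days 0, 14 and 28, naming PCR and ELISA only.
- Appendix A1, a single table for all DHCWs: three POC marks, two PCR marks and two ELISA marks.

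**The concern.** Section 6 is the study schedule and is set out by office type, so a practice could reasonably work from it. A LAB office that did so would give its DHCWs an unplanned antigen swab at Day 14 and would need point-of-care kits. It would skip the mid-study saliva PCR procedure: collection on a Monday or Wednesday, packaging and shipping (7.2.3), with results within a week (7.2.2). Under Section 7, Day 14 is also the only LAB DHCW visit with saliva alone.

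Those DHCWs would have met both kinds of test before answering the end-of-study questions on testing preference and logistics. The study's purpose is to find out whether each set of procedures works in an office, so it matters which procedure was carried out.

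Whichever section an office follows, it departs from the other. The exemptions in 8.1.3 and 15.6 cover incomplete visits, activities outside their windows, and missing surveys, forms or data. They do not mention substituting one test for another.

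**Working it through.** The plan gives no figure for this point, and Section 11 states that no sample size was calculated. The check is a comparison of the text followed by a head count.

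**Step 1: Day 14 test for LAB-office DHCWs, by location**

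| Place | Test indicated |
|---|---|
| 6.1, LAB table | POC |
| 7, Group 3 | PCR on self-collected saliva |
| 7.1, Group 3 testing row (Days 0, 14, 28) | PCR and ELISA only |
| 7, Group 3 footnote | Laboratory-processed test only |
| 5.3 table | Virus and antibody, no antigen (day not given) |
| 4 | Saliva-based laboratory viral test (day not given) |

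Only 6.1 assigns a point-of-care test to this group. Its row matches the POC-office row word for word, so a copying slip is the natural explanation, although the document does not confirm it.

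**Step 2: Appendix A1.** Section 7 needs PCR at Days 0, 14 and 28, so three marks; the appendix has two. Its column headings were scrambled when the PDF was read, so only the count is used. The three POC marks are what POC offices need and are not evidence either way.

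**Step 3: size.** Inputs from 5.3: two LAB offices, each with the member dentist plus 4 to 9 others. DHCWs per office: n = 1 + 4 = 5 up to n = 1 + 9 = 10. Assume equal office sizes and no withdrawals. An office following Section 7 does 3 PCR visit-tests per DHCW; an office following 6.1 does 2.

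| LAB offices following 6.1 | Wrong-type Day 14 tests | LAB DHCW PCR visit-tests |
|---|---|---|
| 0 | 0 | 2 × 3n = 6n = 30 to 60 |
| 1 | n = 5 to 10 | 3n + 2n = 5n = 25 to 50 |
| 2 | 2n = 10 to 20 | 2 × 2n = 4n = 20 to 40 |

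For each affected DHCW, one of three virus or antigen tests is of the wrong type.

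**Step 4: what does not change**

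- PCR and ELISA at Days 0 and 28 are scheduled in both sections.
- The Day 14 window is the same in both, so the measure of activities within the window can be scored.
- DHCWs rate ease and timeliness once, at Day 28 (3.0).
- Section 11.1 lists only completeness for the Testing Case Report, and neither positivity nor immuno-conversion.
- The 7.1 Group 3 row describes no POC result entry, but 15.2 gives a general DHCW route, so a result could still be recorded.
- Under Reporting and Notification in Section 7, antigen-positive and viral-positive DHCWs are referred in the same way.

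**Side note.** Objective 3 in 3.3 gives a two-weekly time frame for immuno-conversion, under a heading for full-study exploratory outcomes. Sections 6.1 and 7 and Appendix A1 agree on two ELISA draws. This needs only a clarifying phrase.

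**The case against.** The best case against this point is that little follows from it. The intended test can be worked out, and Section 4 already sends the reader to Section 7. Saliva PCR is still tried in LAB DHCWs at Days 0 and 28, with the same packaging, shipping and turnaround, so omitting Day 14 loses a repetition rather than the only trial of the procedure. LAB patients also give saliva alone. Kits are mailed from the Rutgers Clinical Research Center (7.2.2), all personnel are trained in the protocol and each instrument is reviewed (Section 13), so a LAB office running antigen tests unnoticed is less plausible.

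It can also be said that the direction is not certain. The two PCR marks in Appendix A1 fit 6.1 better than Section 7, and 7.2.1 says in general terms that DHCWs may have POC, PCR and/or antibody tests.

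The limits on consequence stand and are reflected in the verdict. The rest does not remove the conflict. The reference to Section 7 is a pointer, not a rule of precedence. Nothing says that kit supply is restricted by office type. Section 7.2.1 covers both office types together and assigns POC to neither. Appendix A1 pools the office types and cannot outweigh Sections 4, 5.3, 7 and 7.1. Because the copying slip is inferred, the sponsor should confirm the intended test when making the correction.

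**Conclusion.** The concern holds. For LAB-office DHCWs at Day 14, Sections 6.1 and 7 order different tests. The weight of the text favours saliva PCR, so the 6.1 row should be treated as the error. Appendix A1 is also one PCR mark short.

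The size is 0 to 20 Day 14 tests of the wrong type, and 20 to 60 LAB DHCW PCR visit-tests in all, where Section 7 plans 30 to 60. These ranges assume 5 to 10 DHCWs in each LAB office and no withdrawals. How many offices would follow 6.1 is unknown, so all three cases are shown.

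The fault concerns which procedure is tried out. It does not alter any listed estimate or the handling of positive results. It should be fixed, with high confidence in the 6.1 conflict; the appendix part rests on the count of marks alone.

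**What to change.** - In the Mid-Study row of the 6.1 LAB-office table, replace the point-of-care test with a self-collected saliva specimen for PCR, after confirming that this is the intended test.
- Split Appendix A1 by office type: PCR at Days 0, 14 and 28 for LAB DHCWs, and POC at Days 0, 14 and 28 for POC DHCWs.
- As a minor clarification, state that the immuno-conversion time points in this feasibility study are Day 0 and Day 28 only.

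The cost is a wording amendment to one table row and one appendix table, plus one phrase. No test, specimen or visit is added to what Section 7 already requires.
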